## 7.2 Primary and Secondary Endpoints/Outcome Measures

This is a pilot study and as such, primary outcome measures are N/A. See above for our primary and secondary objectives. These will be used to inform what our primary outcomes will be in a future trial.

## 8. STUDY PARTICIPANTS

### 8.1 Study Setting

Firstly, the Extreme Environments Laboratory at the University of Portsmouth has a 30 year history of conducting innovative human research trials. The laboratory contains some of the world's leading facilities for conducting environmental research including three bespoke environmental chambers, with temperature, humidity, solar, wind and hypoxia control, and a research group involving over 20 academics and researchers. Two of the applicants (Drs [name] and [name]) have extensive experience of conducting examinations of cold sensitivity and endothelial function in both healthy and clinical populations ([name], Golden, & Tipton, 2013; Hope et al., 2014; Maley, House, Tipton, & [name], 2015). [name] also has significant experience working with patient groups, including several rheumatic conditions and in assessing endothelial function etc. in current research. Presently, the team are completing similar research on individuals with cold sensitivity and the proposed methodology, including infrastructure, equipment and expertise, is therefore feasible and requires no additional training or time to develop.

### 8.2 Overall Description of Study Participants

Participants with a clinical diagnosis of Primary or Secondary Raynaud's Phenomenon.

### 8.3 Eligibility Criteria

#### **Inclusion Criteria**

The participants must meet ALL of the following criteria to be considered eligible for the study:

- Male or Female, aged 18 years or above.
- Diagnosed with Raynaud's Phenomenon.
- Participant is willing and able to give informed consent for participation in the study.

#### **Exclusion Criteria**

The participant may not enter the study if ANY of the following apply:

- Patients with significant renal impairment (eGFR<30),

- Uncontrolled hypertension,
- Taking regular organic nitrates, nicorandil, or thiazolidinidiones,
- or any medication which may interfere with data interpretation or safety,
- who have had a myocardial infarction or cerebro-vascular event,
- who smoke,
- or any other serious medical condition which would interfere with data interpretation or safety will be excluded from participation.

## 9. SAMPLING

Twenty-five individuals with RP would need to be recruited in order to estimate a moderate to large effect size in a pilot study (Johanson & Brooks, 2009). Therefore, we aim to recruit 30 individuals (at a rate of 1 per week) with RP to account for a 15% drop-out rate (typically seen in our clinical trials). We will utilise an opportunistic sampling process, from both clinics and posters and word of mouth.

## 10. STUDY PROCEDURES

*Endothelial function test:* Following a 30 minute acclimatisation period, acetylcholine (ACh) and sodium nitroprusside will be delivered transdermally using iontophoresis to three sites, the middle phalanx of the middle finger of the left hand, the dorsal aspect of the left foot and the volar aspect of the left forearm. Cutaneous vascular conductance and skin temperature will be measured to determine the dose response to ACh at each site separately (Maley et al., 2015).

*Cold challenge test:* Following a 15 min acclimatisation period, participants will undertake light exercise on a cycle ergometer for 12 min (maximum of 50 W, to elevate their core temperature by approximately 0.3°C). Prior exercise has been found to increase the reproducibility of the test ([name] et al. 2005) by removing the effect of varying central vasoconstrictor tone. Participants will then undertake a standardised cold challenge test by immersing their hand and foot separately into 15°C water for 2 minutes followed by spontaneous rewarming for 10 minutes ([name] et al., 2013; Hope et al., 2014). Skin

temperature (from a thermal imaging camera), peripheral (skin) blood flow (laser Doppler) thermal sensation, comfort and pain will be measured throughout the test.

*Quality of life:*

Quality of life will be examined through the provision of the Medical Outcomes Study 36-item Short Form Health Survey (SF-36) (Ware Jr & Sherbourne, 1992). The SF-36 measures eight aspects of quality of life: physical functioning, bodily pain, role limitations due to physical health problems, role limitations due to personal or emotional problems, emotional well-being, social functioning, energy/fatigue, and general health perceptions. The SF-36 also provides a single item score that indicates a perceived change in health. The SF-36 has been shown to be reliable with Cronbach alpha scores ranging from .80 to .92 for various aspects of quality of life (Ruta, Abdalla, Garratt, Coutts, & Russell, 1994). This will be measured at each experimental visit post CBJ or placebo consumption.

*Qualitative analysis (acceptability):*

Semi-structured interviews will be used to examine the acceptability of CBJ and placebo supplementation. Specifically, interviews will explore research methods / testing procedures and the participant experience of consuming beetroot juice regularly. Approximately 15-20 semi-structured interviews will be necessary to reach a point of data saturation where no new information is provided. Interviews will be conducted by a researcher with experience (co-applicant) in qualitative research methods and methodologies. Interviews will be transcribed verbatim and analysed thematically (Braun & Clarke, 2006).

### 10.1 Recruitment

Participants will be recruited from a database of known individuals with RP who attend outpatient clinics at the Queen Alexandra Hospital (Portsmouth) and via posters and word of mouth within the University of Portsmouth. If this study is funded, a research nurse will be utilised to find potential participants.

### 10.2 Screening and Enrolment

*Consent and Screening:* Visit 1 will act as a screening, consent and baseline assessment (3.5-4 hours).

Participants will be given the opportunity to ask any questions they may have after reading the participant information sheet. A standard medical history and clinical examination will be undertaken by a research nurse or member of the research team, including for example height, mass, electrocardiogram, ankle-brachial pressure index and blood sample collection for lipids and biochemical markers, urea and electrolytes, and liver function tests. Seated resting blood pressure measurements will be performed to calculate systolic, diastolic blood pressure and cutaneous vascular conductance (flux/MAP). If this study is funded, a research nurse will be utilised to find and screen potential participants.

#### 10.3 Randomisation

During the first visit the participants will be randomised by a nurse to begin either the CBJ or placebo arm of the study. A computer programme will be utilised to randomly allocate to treatment order, whilst stratifying for disease type and gender. Participants will be provided with instructions and their first acute dose to take away with them.

#### 10.4 Study Assessments

*Endothelial function test:* Following a 30 minute acclimatisation period, acetylcholine (ACh) and sodium nitroprusside will be delivered transdermally using iontophoresis to three sites, the middle phalanx of the middle finger of the left hand, the dorsal aspect of the left foot and the volar aspect of the left forearm. Cutaneous vascular conductance and skin temperature will be measured to determine the dose response to ACh at each site separately (Maley et al., 2015).

*Cold challenge test:* Following a 15 min acclimatisation period, participants will undertake light exercise on a cycle ergometer for 12 min (maximum of 50 W, to elevate their core temperature by approximately 0.3°C). Prior exercise has been found to increase the reproducibility of the test ([name] et al. 2005) by removing the effect of varying central vasoconstrictor tone. Participants will then undertake a standardised cold challenge test by immersing their hand and foot separately into 15°C water for 2 minutes followed by spontaneous rewarming for 10 minutes ([name] et al., 2013; Hope et al., 2014). Skin temperature (from a thermal imaging camera), peripheral (skin) blood flow (laser Doppler) thermal sensation, comfort and pain will be measured throughout the test.

## Secondary Objectives

### *Quality of life:*

Quality of life will be examined through the provision of the Medical Outcomes Study 36-item Short Form Health Survey (SF-36) (Ware Jr & Sherbourne, 1992). The SF-36 measures eight aspects of quality of life: physical functioning, bodily pain, role limitations due to physical health problems, role limitations due to personal or emotional problems, emotional well-being, social functioning, energy/fatigue, and general health perceptions. The SF-36 also provides a single item score that indicates a perceived change in health. The SF-36 has been shown to be reliable with Cronbach alpha scores ranging from .80 to .92 for various aspects of quality of life (Ruta et al., 1994). This will be measured at each experimental visit post CBJ or placebo consumption.

### *Qualitative analysis (acceptability):*

Semi-structured interviews will be used to examine the acceptability of CBJ and placebo supplementation. Specifically, interviews will explore research methods / testing procedures and the participant experience of consuming beetroot juice regularly. Approximately 15-20 semi-structured interviews will be necessary to reach a point of data saturation where no new information is provided. Interviews will be conducted by a researcher with experience (co-applicant) in qualitative research methods and methodologies. Interviews will be transcribed verbatim and analysed thematically (Braun & Clarke, 2006).

### *Biochemical analysis:*

Blood / saliva samples will be taken and assessed prior to testing on each study visit. Blood samples for plasma nitrate/nitrite will be taken in chilled Lithium Heparin tubes and EDTA tubes for assessment of oxidative stress markers. The blood / saliva needs to be placed in a chilled (4°C) centrifuge and spun at 4000g for 10 minutes immediately on collection. Once spun the plasma or saliva will be pipetted into aliquots. The samples will be placed in a -20°C freezer prior to transfer to a -80°C freezer for storage at the end of each day.

Deproteinised samples will be analysed for nitrite and nitrate concentration using a Sievers nitric oxide analyser (Sievers NOA 280i, Analytix Ltd, Durham, UK) and a modification of our previous chemiluminescence technique. Elisa's will be utilised using commercially available

assays for markers of oxidative stress such as glutathione and nitrotyrosine. We will also measure plasma for the quantification of endothelin 1.

#### 10.5 Discontinuation/Withdrawal of Participants from Study Treatment

Participants may be withdrawn from treatment, or from the study as a whole; if they ask to withdraw, if participant safety is in question or if the study is stopped early.

#### 10.6 Definition of End of Study

The end of study will be the date of the last visit of the last participant.

### 11. INTERVENTIONS

#### 11.1 Description of Study Intervention / Treatment

*Visit 2 and 4 (acute supplementation visits ~ 3 hours).* One and a half hours before visits 2 and 4, participants will be instructed to ingest an acute dose of 140 ml of either CBJ (delivers ~ 12.4 mmol·L of inorganic nitrate) or placebo (~ 0.002 mmol·L Beet It, Heartbeet Ltd.). The primary objectives (peripheral blood flow, endothelial function and skin temperature; see below for details) will be assessed ~ 1.5 hours after arrival in the research facility. The timing of the supplement is key to ensure plasma nitrate and nitrite are elevated throughout the testing period (Webb et al., 2008). On arrival at the laboratory, the participants will have their BP measured and a ~ 20 ml venous blood sample taken for determination of plasma [nitrate], [nitrite] and nitrotyrosine and protein carbonyl concentrations (which are clinically relevant markers of oxidative stress (Frijhoff et al., 2015)). The participants will then undertake an endothelial function (iontophoresis) test in an ambient temperature of 23°C followed by a cold challenge in an ambient temperature of 30°C (both described below). Visits 3 and 4 (crossover period) will be separated by at least 7 days to allow washout (Wylie et al., 2013) and all visits will be conducted at the same time of day in a counter-balanced order at a time suitable for the participants.

*Visit 3 and 5 (chronic supplementation visits ~ 3 hours).* Visits 3 and 5 will be identical in nature to visit 2 and 4, however, following chronic supplementation of 70 ml·day of either CBJ or placebo for 14 days (Vanhatalo et al., 2010; Wylie et al., 2013). With consent,

participants will be reminded to take the juice via text message or voice mails. Please see the accompanying documents for the participant flow through the study.

The participants diet will be standardised prior to testing and they will be asked to abstain from using antibacterial mouth wash for 7 days prior to each test and during the testing phase as this has been shown to reduce the concentration of oral microflora that are responsible for the reduction of nitrate to nitrite (Govoni et al., 2008). Participants will also be asked to refrain from using other medicines during the testing period that may affect blood flow or the release of nitrite from the CBJ with such as organic nitrates, proton pump inhibitors, ranitidine and nicorandil.

#### 11.2 Adherence to Study Treatment

Venous blood samples will be taken on all visits. Deproteinised samples will be analysed for nitrate and nitrite concentration using a Sievers nitric oxide analyser (Sievers NOA 280i, Analytix Ltd, Durham, UK) with our established technique (S. [name], J et al., 2010; S. [name], J et al., 2009; S. J. [name], Wilkerson, DiMenna, & Jones, 2009; M [name] et al., 2013; Mark [name] et al., 2014; Anthony I [name] et al., 2015; Anthony I. [name] et al., 2015; [name] et al., 2016). This will essentially provide strong evidence of adherence to the supplement.

#### 11.3 Accountability of the Study Treatment

This study is double-blind in nature. The research nurse (if funded) or technicians from the department of Sport and Exercise Science at the University of Portsmouth will dispense the CBJ. At each time the CBJ is dispensed, the juice will be checked for treatment arm and double signed by 2 trained staff members.

#### 11.4 Concomitant Medication / Therapies

Participant involvement is anticipated to be ~6 weeks. Medication will be recorded on enrolment and updated throughout their time on supplementation.

## 12. ASSESSMENT OF SAFETY (IF APPLICABLE)

### 12.1 Definitions

A serious adverse event is any untoward medical occurrence that:

- Results in death,
- Is life-threatening,

NOTE: The term "life-threatening" in the definition of "serious" refers to an event in which the participant was at risk of death at the time of the event; it does not refer to an event which hypothetically might have caused death if it were more severe.

- Requires inpatient hospitalisation or prolongation of existing hospitalisation,
- Results in persistent or significant disability/incapacity, or
- Is a congenital anomaly/birth defect.
- Other important medical events\*

\*Other events that may not result in death, are not life threatening, or do not require hospitalisation, may be considered a serious adverse event when, based upon appropriate medical judgement, the event may jeopardise the participant and may require medical or surgical intervention to prevent one of the outcomes listed above.

### 12.2 Reporting Procedures for Serious Adverse Events

A serious adverse event (SAE) occurring to participant should be reported to the REC that gave a favourable opinion of the study where in the opinion of the Chief Investigator the event was: 'related' – that is, it resulted from administration of any of the research procedures; and 'unexpected' – that is, the type of event is not listed in the protocol as an expected occurrence. Reports of related and unexpected SAEs should be submitted within 15 days of the Chief Investigator becoming aware of the event, using the NRES report of serious adverse event form (see NRES website).

### 12.3 Recording and Reporting Procedures for All Adverse Events

All adverse events will be recorded in participant file notes. Distinction between SAE and AE will be made by an independent medical officer. All SAE will be reported to the sponsor and the REC regardless of if it is related or not.

## 13. DATA HANDLING AND RECORD KEEPING

### 13.1 Data Collection Forms

Visit 1 will act as a screening, consent and baseline assessment (4 hours). All measures for this visit will be stored in the clinical records folder (CRF). Separate forms will be prepared for; anthropometrics, medical history, screening (i.e. blood pressures etc) and blood markers. On subsequent visits data forms will be used to collect temperatures of the labs and the rewarming of the hands and feet and also for the iontophoresis test. All paper copies will be stored in the CRF's.

### 13.2 Data Management

All study data will be entered on paper copies and stored in participant CRF's. All data will be double data entered into excel / access. Macro's will be used to check for anomalies and corrected. The participants will be identified by a study specific participants number and/or code in any database. The name and any other identifying detail will NOT be included in any study data electronic file. The chief investigator ([name]) is responsible for database maintenance and management.

## 14. DATA ANALYSIS

### 14.1 Description of Analysis Populations

This is a pilot study. All participants who complete all 5 visits will be entered into the analysis as per protocol.

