### 6.2 Secondary Objectives

Secondary objectives: 1) Does CBJ reduce perceived discomfort and pain; 2) is our protocol acceptable to individuals with RP (i.e. cold water stimulus, CBJ palatability) and feasible to perform in a future multi-centre randomised control trial (RCT); and 3) to establish recruitment and retention rates. Resulting estimated effect sizes in relation to their confidence intervals from our primary objective(s) measures will be utilised to identify our primary outcome measure and to power a larger, definitive, multi-centre randomised, control trial.

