*Visit 2 and 4 (acute supplementation visits ~ 1.5-2 hours).* One and a half hours before visits 2 and 4, participants will be instructed to ingest an acute dose of 140 ml of either CBJ (delivers ~ 12.4 mmol·L of inorganic nitrate) or placebo (~ 0.002 mmol·L Beet It, Heartbeet Ltd.). The primary objectives (peripheral blood flow, endothelial function and skin temperature; see below for details) will be assessed ~ 1.5 hours after arrival in the research facility. The timing of the supplement is key to ensure plasma / saliva nitrate and nitrite are elevated throughout the testing period (Webb et al., 2008). On arrival at the laboratory, the participants will have their BP measured and a ~ 20 ml venous blood sample taken. The participants will then undertake an endothelial function (iontophoresis) test in an ambient temperature of 23°C followed by a cold challenge in an ambient temperature of 30°C (both described below). The SF-36 will also be measured here. Visits 3 and 4 (crossover period) will be separated by at least 7 days to allow washout (Wylie et al., 2013) and all visits will be conducted at the same time of day in a counter-balanced order at a time suitable for the participants.

*Visit 3 and 5 (chronic supplementation visits ~ 1.5-2 hours).* Visits 3 and 5 will be identical in nature to visit 2 and 4, however, following chronic supplementation of 70 ml·day of either CBJ or placebo for 14 days (Vanhatalo et al., 2010; Wylie et al., 2013). With consent, participants will be reminded to take the juice via text message or voice mails. Please see the accompanying documents for the participant flow through the study.

The participants diet will be standardised prior to testing and they will be asked to abstain from using antibacterial mouth wash for 7 days prior to each test and throughout the period of testing as this has been shown to reduce the concentration of oral microflora that are responsible for the reduction of nitrate to nitrite (Govoni, Jansson, Weitzberg, & Lundberg, 2008). Participants will also be asked to refrain from using other medicines during the testing period that may affect blood flow or the release of nitrite from the CBJ with such as organic nitrates, proton pump inhibitors, ranitidine and nicorandil.

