### 14.2 Analysis of Endpoints

All data will be tested for normality. Where data are not normally distributed a nonparametric test will be performed. Data will be presented as means  $\pm$  SD. Statistical analyses will be performed on SPSS software version 22.0 (Chicago, IL). Statistical difference will be accepted when  $P < 0.05$ . Statistical differences will be assessed by repeated-measures

ANOVAs. Where baseline differences are present, analyses of covariance (ANCOVAs) will be used with baseline as a covariate.

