#### 14.3 Procedure for Dealing with Missing, Unused and Spurious Data

Where statistic differences are present, post hoc (Bonferroni-corrected) analysis will be performed. Outliers will remain within the data. Within the data analysis software missing data will be coded 9999 and the data point missed during analysis.

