#### 14.4 Procedures for Reporting any Deviation(s) from the Original Statistical Analysis Plan

For this pilot a SAP is not required (excluding the above).

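### Section 14.1 admits only five-visit completers, so a complete acute pair (Visits 2, 4) or chronic pair (Visits 3, 5) is lost when a visit outside that pair is missed

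*Combined protocol and SAP*

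**What the plan says.** Section 14.1 states that "All participants who complete all 5 visits will be entered into the analysis as per protocol". It says all such participants rather than only such participants, but no all-randomised, available-data or per-contrast set appears anywhere. Section 14.4 rules out a fuller plan: "For this pilot a SAP is not required (excluding the above". Completers-only is therefore the operative rule.

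Section 7.1 makes Visits 2 and 4 the acute visits, one in each period. The chronic visits each come after two weeks of daily juice: "Visits 3 and 5 will be identical in nature to visit 2 and 4, however, following chronic supplementation of" (the sentence then gives the daily volume and the duration). The crossover falls between the two halves: "Visits 3 and 4 (crossover period) will be separated by at least 7 days to allow washout".

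Section 14.2 names repeated-measures ANOVA without giving its factors, with a nonparametric alternative, and adds: "Where baseline differences are present, analyses of covariance (ANCOVAs) will be used with baseline as a covariate". Section 14.3 says: "Within the data analysis software missing data will be coded 9999 and the data point missed during analysis".

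Section 6.2 says that the results will serve to size the definitive trial and, before that, to settle its main endpoint: "Resulting estimated effect sizes in relation to their confidence intervals from our primary objective(s) measures will be utilised to identify our primary outcome measure".

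**The concern.** Each contrast needs two visits, yet 14.1 requires all five. A participant with Visits 2 and 4 who misses Visit 3 or 5 has everything the acute contrast needs and is still excluded. The same applies to a participant with Visits 3 and 5 who misses Visit 2 or 4, for the chronic contrast. Section 14.3 does not repair this, because skipping a missing data point does not readmit a person whom 14.1 has left out.

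Two things are at stake. The first is precision: effect sizes and confidence intervals are the pilot's main product, and they would be wider than the collected data allow. The second is selection: the estimates would describe only people who managed every visit, in a study that also sets out to measure retention and acceptability.

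There is a related ambiguity. If the ANOVA in 14.2 is run as one model over the four treated visits, one missing value removes the participant for that outcome, which is not what 14.3 suggests. As 14.2 does not give the layout, this is unclear rather than a proven contradiction.

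**Working it through.** **Inputs from the protocol.** Section 9: target 25, recruitment 30, drop-out 15%. Section 7.1: two 14-day supplementation phases and a washout of at least 7 days. Section 11.4: "Participant involvement is anticipated to be ~6 weeks", that is 42 days. The timing of drop-out is not given.

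**The plan's own figure.** 25/(1 − 0.15) = 29.4, rounded up to 30. This reproduces. Expected completers: 30 × 0.85 = 25.5. Expected drop-outs: 30 × 0.15 = 4.5.

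**Acute contrast, loss against a pair rule.** If a share *s* of drop-outs leaves between Visits 4 and 5, the available acute pairs number 25.5 + 4.5*s*. The relative increase in standard error (SE) from using completers is √[(25.5 + 4.5*s*)/25.5] − 1.

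Visit 2 to Visit 5 takes 14 + 7 + 14 = 35 days, which leaves about 7 of the 42 days before Visit 2 (inferred). With drop-out proportional to time (assumed), *s* = 14/42 = 0.333.

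| Assumed timing of drop-out | *s* | Acute pairs | SE increase |
|---|---|---|---|
| None after Visit 4 | 0 | 25.5 | 0% |
| 80% before Visit 3 | 0.10 | 25.95 | 0.9% |
| Even over the four intervals | 0.25 | 26.6 | 2.2% |
| Proportional to time, 42 days | 0.333 | 27.0 | 2.9% |
| Proportional to time, none before Visit 2 (14/35) | 0.40 | 27.3 | 3.5% |
| Half between Visits 3 and 4, half after Visit 4 | 0.50 | 27.75 | 4.3% |
| All after Visit 4 | 1 | 30.0 | 8.5% |

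Allowing the number of drop-outs to vary raises the last two rows to 4.4–4.6% and 8.7–9.0%. In units of the SD of paired differences, the 95% confidence interval half-width t(0.975, n − 1)/√n is 0.408 at n = 25.5 and 0.396 at n = 27.

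**Chronic contrast, loss against a pair rule.** A participant who has dropped out never has Visit 5, so the loss from drop-out is 0%.

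**Isolated missed visits.** If each treated visit is missed independently with probability *p*, completers number in proportion to (1 − *p*)⁴ and pairs to (1 − *p*)². The SE ratio is 1/(1 − *p*): 1.010, 1.020 and 1.053 for assumed *p* of 1%, 2% and 5%. This applies to either contrast, on top of drop-out.

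**Loss against a mixed model on all available data.** Generalised least squares with known variances was simulated with 15 per sequence and 15% random drop-out. Within-person correlation was assumed at 0.5 or 0.6, and participant-by-period variance at 0%, 10% or 30% of the within-person variance.

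| Assumed timing | Acute | Chronic |
|---|---|---|
| 80% before Visit 3 | 2.0–2.3% | 0.6–0.9% |
| Even | 3.4–3.7% | 1.5–1.9% |
| Proportional to time | 4.2–4.5% | 1.7–2.2% |
| Half Visits 3–4, half after Visit 4 | 5.8–6.1% | 3.2–3.7% |
| All after Visit 4 | 8.9–9.2% | 3.4–4.5% |

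A repeat run agreed within simulation error. Because the variances are treated as known, these figures are upper guides to what a fitted model would recover.

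**The case against.** The strongest reply is that this is a small matter. The sample size already budgets for completers, 25.5 exceeds 25, and the expected acute gain is only about 1 to 1.5 participants. A common completer set also has some merit: effect sizes compared to choose a primary outcome then come from the same people. All of this stands, and it limits the weight of the point.

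The two halves are not equally likely. Losing a complete chronic pair requires someone to skip Visit 2 or 4 and then carry on. Section 7.1 schedules visits at times that suit the participant, and section 16.1 offers weekend testing in response to concerns about five 3-hour visits, so some missed visits could be rearranged. The protocol gives no missed-visit rate. The 1%, 2% and 5% are illustrations. Added to 15% drop-out, they would leave 24.5, 23.5 and 20.8 completers (25.5 × 0.99⁴, 0.98⁴ and 0.95⁴), all below 25. No attrition beyond the budgeted 15% is claimed.

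The pair rule is itself a completer rule within each contrast. It does not change who enters the chronic comparison when the loss is drop-out, so it does little for selection there. Only a model on all available data would, and that relies on data being missing at random.

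Finally, if a single four-visit ANOVA is intended, the model would drop incomplete participants anyway. That is a reason to settle 14.2 and 14.3 together with 14.1, not to leave 14.1 as it is.

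**Conclusion.** The concern holds. Followed as written, 14.1 discards complete treatment pairs that have already been collected, and nothing else in the plan brings them back.

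The size is modest. The acute SE is about 3% larger than under a pair rule if drop-out is proportional to time, and 0.9–4.5% larger under the other mixed timings. The extremes are 0% and about 9%. The chronic contrast loses nothing to drop-out under the pair rule and about 1–4% against a mixed model. Occasional missed visits would add a little to both. Every one of these figures rests on assumed timing or rates. The 15% and the targets of 25 and 30 are the protocol's.

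Whether completer selection biases the effect sizes, and in which direction, cannot be determined from the protocol. The planned sample size is not undermined. The point should be fixed because the remedy is cheap and the estimates feed directly into the definitive trial.

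**What to change.** **Section 14.1.** Analyse each contrast in all randomised participants, by assigned sequence, who have both of its visits: 2 and 4 for acute, 3 and 5 for chronic. Report n for each contrast. Keep five-visit completers as a sensitivity analysis. The same pair sets serve the nonparametric branch of 14.2.

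**Sections 14.2 and 14.3.** State the ANOVA factors, and say what happens to a participant with a missing cell.

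**Alternative.** Fit a mixed model to all available post-dose data with treatment, period, acute/chronic and treatment-by-acute/chronic, plus baseline as covariate where 14.2 calls for it. Use participant and participant-by-period random effects, or an unstructured within-person covariance, with a small-sample degrees-of-freedom method that the software provides. A single participant random effect is not enough. If participant-by-period variance is a share *f* of within-person variance, the true SE exceeds the reported one by a factor 1/√(1 − *f*/3) for the acute contrast, which is 1.017–1.054 for *f* = 0.1–0.3. For the effect averaged over acute and chronic the factor is √[(1 + *f*)/(1 − *f*/3)], or 1.067–1.202.

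**Cost.** Rewording of 14.1 to 14.3, with no new participants, visits or measurements. The downsides are slightly more analysis work, slightly different participants in the two contrasts, and a missing-at-random assumption to state if the mixed model is used.
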